### 1.1 Study Hypothesis and Rationale

Bonner *et al* investigated the benefit of the addition of cetuximab to radiation. It was concluded that cetuximab improves locoregional control and reduces mortality without increasing the common toxic effects associated with radiotherapy to the head and neck. In our study, we propose to select locally advanced head and neck cancer patients, who are older than age 70 or are not deemed candidates for chemotherapy. This group was not extensively investigated in the earlier randomized trial, in that

---

 Abbreviations: **CR**, complete response; **EGFR**, epidermal growth factor receptor; **MAPK**, mitogen-activated protein kinase; **PI3K**, phosphatidylinositol 3-kinase; **PR**, partial response; **RT**, radiation treatment/therapy; **STAT**, signal transducer and activator of transcription; **TMA**, tissue microarray.

90% of patients in the Bonner study had a KPS of 80 or greater, and the median age of the patients was 57. The primary end-point of this trial is to characterize local progression free survival in these patients, when treated with cetuximab+radiation.

We also propose to develop a molecular pharmacodynamic predictor of local control after treatment with combination cetuximab-radiation. We hypothesize that tumor EGFR degradation and other markers of down-stream EGFR inhibition as well as novel phosphoproteomic markers observed in tumor biopsies taken 7 days after the administration of cetuximab, will predict the effectiveness of cetuximab-radiation. The first biopsy will be obtained prior to administration of the loading dose of cetuximab. Prior to initiation of cetuximab concurrent with radiation, on Day 7, following the cetuximab loading dose, a tumor biopsy for the biomarkers will be obtained. We hypothesize that tumors that do not demonstrate the changes that correlate with response after cetuximab in the *in vivo* preclinical studies are more likely to progress following cetuximab-radiation therapy compared to those that show changes that correlate with response. If our hypothesis is validated, we will gain a tool that will help identify patients who are most likely to benefit from radiation and cetuximab, a very expensive and moderately toxic treatment.

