Although the focus for developing a predictive assay has been on assessing pretreatment paraffin embedded specimens, it seems possible that a predictive assay may require determining the response to treatment (i.e. a pharmacodynamic endpoint). As has been noted by Mendelsohn and Balsega, successful application of EGFR targeted therapy may require not only the presence of activated EGFR, but also that the cancer depends on this pathway for cell survival. This dependence (“addiction”) might be best determined not simply by assessing pretreatment specimens, but by comparing pre- and post-treatment specimens to determine if the inhibitor has actually inhibited both EGFR phosphorylation and downstream signaling. Indeed, a substantial literature has elucidated these EGFR signaling pathways, which offers candidate molecules. Our preclinical data and the literature

suggest that changes in total EGFR, pEGFR, pSTAT3, and Bcl-XL, EGFR copy number, EGFRvIII status, and NFκB may predict response to cetuximab-radiation. Additionally, we postulate that EGFR variant 3 (EGFRvIII) expression may predict response to cetuximab, since tumors that express primarily this variant are less likely to respond to cetuximab blockade than tumors that express the full length receptor. The vIII form is reported to be intrinsically active and thus blocking ligand binding with the antibody should not be effective. Sok et al. reported that 42% of head and neck tumors in their series expressed EGFRvIII. We will assess vIII expression using RT-PCR with RNA isolated from the research biopsy.

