#### 13.0 EGFR analysis (General Laboratory Guidelines)

The primary goal of this analysis is to determine whether cetuximab given at the clinically recommended dose, will inhibit EGFR phosphorylation and down-stream signaling effects within the tumor as well as the normal mucosa following therapy. In addition, the activation of EGFR and various down-stream signaling markers will be measured using immunoblotting as well as immunohistochemical analysis in both normal and tumor samples at baseline and post-treatment.

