#### 13.5

##### Method of Assessment of EGFR Expression in Tumor After Cetuximab

##### Loading Dose

At the time of the second biopsy, four core biopsies from different areas of the tumor as well as swab of the normal appearing mucosa will be obtained. Four core biopsies will be processed with one core used in high-throughput immunoblot analysis, one core will be fixed in formalin to be embedded in paraffin, one core will be frozen and fixed in Tissue-Tek OCT for immunofluorescence analysis and one core will be used for RNA and DNA isolation using Trizol. EGFR phosphorylation analysis using immunoblotting and immunohistochemistry will be performed in the surgical specimen and immunofluorescence analysis will also be performed if sufficient tissue is available using standard methods. Interpretations of the staining will be performed according to the standard guidelines. The EGFR and critical associated down-stream signaling pathways will be analyzed post- induction therapy, including p-EGFR and total EGFR, p-ERK1/2, p-AKT, p27, Ki-67, and p-STAT3, and other markers that we may discover in our preclinical studies. EGFRvIII expression and p53 mutation analysis will be assessed on cDNA obtained from total RNA converted with RT-PCR. Genomic DNA from the tumor biopsy will be used to test for HPV presence and type as carried out by PCR-mass spect using the AttoSense assay at SensiGen, LLC.

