## 21.0 Statistical Considerations

**21.1** General Description: This is a single-arm, Phase II trial to characterize the clinical outcome of standard of care, cetuximab concurrent with radiation, in a special population (head and neck cancer patients who cannot tolerate concurrent chemoradiotherapy due to advanced age, poor performance status or concurrent illness), and to determine if biomarker response to a loading dose of cetuximab is predictive of that outcome.

**21.2** Number of patients: Fifty evaluable patients will be accrued to the trial, which is expected to take 36 months. A patient will be evaluable for the primary objectives if he or she undergoes Research Biopsy #1 and #2 and either completes the full course of cetuximab+RT or has cetuximab+RT stopped for toxicity. Unevaluable patients will be replaced.

**21.3** Analysis plan

**21.3.1 Primary Objective 1:** Determine changes in tumor EGFR, pEGFR, downstream signaling and novel phosphoproteins following a loading dose of cetuximab in patients who are poor candidates for chemoradiation (age  $\geq 70$  years or with significant co-morbidities) and are therefore treated with cetuximab+radiation. These markers will be assessed in tumor biopsies harvested before and after the loading dose of cetuximab. The initial analysis will use descriptive and graphical statistics to determine if any of the markers require transformation prior to analysis. Markers may be assessed on a continuous, ordinal or

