dichotomous scale; markers measured on a continuous scale will be analyzed via general linear models (possibly after transformation), while ordinal and dichotomous markers will be analyzed via cumulative logit and logistic regression analyses, respectively. The primary questions to be answered in this objective are: is the marker modulated by the loading dose of cetuximab; are there baseline clinical or demographic variables that are related to significant variation in biomarker response to the loading dose of cetuximab? For continuous variables, the null hypothesis that the mean value of the change (absolute or percent of baseline) equals zero will be tested by means of a single sample t-test. The second question will be answered by means of analysis of variance on baseline clinical and demographic variables. For dichotomous markers, patients will be stratified into elevated versus not elevated at baseline, and Wald tests on logistic regression parameter estimates will be used to test the null hypothesis that the proportion of patients changing state from baseline is different from 0.5, and to determine if any subset of patients defined by clinical or demographic factors have proportions significantly different from 0.5. Ordinal markers will be handled in a similar fashion.

[figure not shown]
21.3.2 **Primary Objective 2** Characterize clinical outcomes, including local recurrence, progression-free survival and overall survival in these patients, and correlate these clinical outcomes with the changes in tumor EGFR, pEGFR, downstream signaling, and novel phosphoproteins. Logistic regression and proportional hazards (Cox) regression will be used to relate clinical out (local recurrence, progression-free survival or overall survival) to changes in markers across the loading dose. All of the markers will be analyzed, but markers that are modulated by the loading dose (identified in Primary Objective 1) will be of particular interest.

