### **High-throughput immunoblotting and isolation of RNA and DNA for genetic studies:**

Tumor samples are collected and immediately stored in Allprotect Tissue Reagent from Qiagen. They are then divided and one portion is homogenized for protein extraction 45, 46. A total of 200 µg total protein will be subjected to electrophoresis on a 2D 4 to 12% bis-tris precast gel (Invitrogen, Carlsbad, CA) and transferred onto a PVDF membrane. A Miniblotter 28 dual system (Immunelect, Cambridge, MA) will be used to probe all the antibodies in duplicate. After incubating the membrane with different antibodies overnight, membranes will be washed and probed with horseradish peroxidase conjugated IgG (Cell Signaling Technology, Beverly, MA), diluted 1:25,000 in TBST for 1 hr at room temperature; the antigen-antibody complexes will be visualized by enhanced chemiluminescence (ECL-Plus; GE Biosciences, Piscataway, NJ). The films then will be scanned, and the bands analyzed using NIH ImageJ software. Proteins to be assessed include phospho and total forms of EGFR, AKT, Src, STAT3, in addition to total p27, PARP, Bcl-XL and novel proteins for which we have either commercially available or custom-raised antibodies. Isolation of DNA and RNA will be carried out using DNAeasy and RNAeasy (both from Qiagen) on the remaining sample according to the manufacturers instructions.

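### EGFR and pEGFR changes are tested only as separate markers, so if total EGFR falls, a fall in pEGFR cannot be attributed to inhibited phosphorylation rather than receptor loss

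*Combined protocol and SAP*

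**What the plan says.** Section 21.3.1 names EGFR and pEGFR as separate items: "Determine changes in tumor EGFR, pEGFR, downstream signaling and novel phosphoproteins following a loading dose of cetuximab". The question put to each is "is the marker modulated by the loading dose of cetuximab". For continuous markers, the change in absolute or percentage terms is compared with zero in a one-sample t-test, possibly after transformation. Section 21.3.2 then relates the marker changes to local recurrence, PFS and overall survival, with special interest in markers found to be modulated.

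The laboratory goal in section 13.0 is whether cetuximab "will inhibit EGFR phosphorylation and down-stream signaling effects within the tumor". Section 1.3 gives the reason for comparing biopsies before and after treatment: "to determine if the inhibitor has actually inhibited both EGFR phosphorylation and downstream signaling". The hypothesis in section 1.1 begins: "We hypothesize that tumor EGFR degradation and other markers of down-stream EGFR inhibition".

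The data for a relative measure are planned. Section 13.5 covers post-dose markers "including p-EGFR and total EGFR, p-ERK1/2, p-AKT, p27, Ki-67, and p-STAT3". Appendix B (high-throughput immunoblotting) states: "Proteins to be assessed include phospho and total forms of EGFR, AKT, Src, STAT3", with antibodies probed in duplicate. No section divides a phospho form by its total form, adjusts one for the other, or says how to read pEGFR when EGFR also falls. The only relative EGFR analysis, in 21.3.4, compares tumor with normal mucosa.

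**The concern.** The amount of pEGFR is total EGFR multiplied by the fraction phosphorylated. The protocol names two things cetuximab may do, degrade the receptor and inhibit its phosphorylation, and both reduce that product. A test on pEGFR alone responds to either. A separate test on total EGFR shows whether receptor was lost, but two separate tests of mean change do not estimate the change per receptor.

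Two things are at stake. The first is whether the trial can answer the question in section 13.0 if total EGFR falls. The second is how to read 21.3.2: a pEGFR change that predicts outcome might only restate receptor loss, and the plan has no derived value that would show this.

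**Working it through.** **The plan's own figure.** Section 21.4 gives at least 80% power at an effect of 1.1 standard units (50 patients, 36 months' accrual, median 22 months, analysis six months after the last patient, alpha 0.05). Simulating a single-covariate Cox model under these inputs, with about 25 events, gives 84% to 85% at 1.1 and 78% at 1.0. The figure reproduces and does not depend on the point made here.

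**One patient.** Total EGFR goes from 100 to 50, with 20% phosphorylated before and after. Then pEGFR goes from 20 to 10, a 50% fall. The ratio pEGFR/EGFR stays at 0.20.

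**Inputs for 50 patients.** N = 50 is from 21.2 and the one-sample t-test from 21.3.1. Alpha is 0.05, taken as two-sided because the documents do not say. Assumptions not in the documents: receptor loss of 10% to 50% (as a median), and an SD of 0.3, 0.5 or 0.7 for each of two independent components on the log scale.

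**Formulas.** Change in log pEGFR = change in log EGFR + change in log(pEGFR/EGFR). With no mean change per receptor, the mean change in log pEGFR is log(1 − loss). Its SD is √2 × component SD, that is 0.424, 0.707 or 0.990. The noncentrality is |log(1 − loss)| × √50 / SD. For 30% loss and component SD 0.5: 0.357 × 7.07 / 0.707 = 3.57, which gives 94%.

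Chance that the log-scale t-test shows a significant fall in pEGFR:

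| Receptor loss | SD 0.3 | SD 0.5 | SD 0.7 |
|---|---|---|---|
| 10% | 41% | 18% | 11% |
| 20% | 95% | 59% | 35% |
| 30% | 100% | 94% | 70% |
| 50% | 100% | 100% | 99.8% |

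The same test on log(pEGFR/EGFR) rejects in about 5% throughout. It has 94% to 100% power for a true 30% fall per receptor.

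**Dependence on scale.** Section 21.3.1 also allows absolute or percent change. Under the same lognormal model the mean percent change is (1 − loss) × exp(SD²) − 1, with SD the component SD. For 30% loss this is −10% at SD 0.5 and +14% at SD 0.7. A significant fall on the percent scale then appears in about 25% and 2% of trials, against 99% at SD 0.3. With 10% loss and SD 0.7 the mean is +47%, and a significant *rise* appears in 41% of trials (32% on the absolute scale, with an assumed SD of 0.5 for log baseline pEGFR).

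**Outcome models.** With equal component SDs, the log changes in EGFR and pEGFR correlate at 1/√2 = 0.71. I simulated the 21.4 setting with outcome driven only by EGFR change (assumed hazard ratio 2 per SD). Change in pEGFR was significant in 59% of trials, and change in the ratio in about 5%.

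**The case against.** The strongest reply is that the plan asks only whether each marker is modulated. If pEGFR halves, it was modulated, and saying so is correct. Total EGFR is tested beside it, so in the one-patient example a reader would see both halve. The tumor's total pEGFR is also a legitimate measure of net signal. A ratio would show nothing if signalling fell wholly through degradation, which is the mechanism section 1.1 puts forward. All of this stands, and it is why raw pEGFR should stay on the list at full standing.

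Several stronger readings are tempting, but the documents do not support them:

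- A reader might infer that receptor loss will be reported as inhibited phosphorylation. The plan is silent on interpretation and does not commit to that reading.
- The percentages might be taken as an inflated type I error. Under the plan's null of zero mean change in pEGFR they are power to detect a real fall. They count as errors only for a claim about phosphorylation per receptor.
- One might extend the degradation argument to AKT, Src and STAT3. The documents hypothesise degradation of EGFR only, and nothing suggests that the total forms of the others fall.
- EGFR and pEGFR changes might be called one signal. At a correlation of 0.71, half the variance of the pEGFR change is independent of receptor loss.

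What the reply does not remove is the wording of sections 13.0 and 1.3. Both ask about inhibition of phosphorylation, and the planned tests cannot settle that if EGFR also falls.

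**Conclusion.** The point holds as a gap in the derived markers, not as an error in a planned test. If total EGFR falls, a fall in pEGFR cannot be attributed to inhibited phosphorylation rather than to receptor loss. That conclusion follows from the definition of pEGFR amount and needs no assumed figures.

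The frequency does need them. On the log scale, 20% to 50% receptor loss alone gives a significant pEGFR fall in 35% to 100% of trials at component SDs of 0.3 to 0.7. On the untransformed scales the result can be much weaker or even reverse in sign. The loss, the SDs, the independence of the components and the lognormal form are all assumptions. The sample size and the stated power are unaffected. This is a cheap improvement rather than a necessary correction.

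**What to change.** In 21.3.1 add, for immunoblot data only, a derived marker for EGFR, AKT, Src and STAT3: the change from Research Biopsy #1 to #2 in log(phospho/total), with both bands from the same lysate and blot. AKT, Src and STAT3 are included because their total forms are already probed, not because loss is expected. Test the derived change against zero with the planned one-sample t-test and report it beside the raw phospho and total changes. State that any conclusion about inhibited phosphorylation per receptor rests on this ratio, and keep raw pEGFR as the net-signal marker. Enter the ratio as an additional marker in 21.3.2.

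No new tissue, assay or patients are needed. The costs are that the ratio carries the error of two bands and that four markers join the list. The ratio does not apply to the 1-to-4 TMA intensity scores, where a quotient has no clear meaning, or to p-ERK1/2, for which no total form is listed. For those, the plan should say that a phospho change is read as net signal only.

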21.3.3 **Primary Objective 3** *Describe the toxicity, in particular mucositis/dysphagia, of this regimen.* Adverse events will be tabulated by grade (NCI CTCAE v4), category (mucositis and dysphagia are expected to be the most common) and relatedness to treatment (not, unlikely, possibly, probably or definitely). The proportion of patients experiencing Grade 3 or worse adverse events at least possibly related to treatment will be calculated, accompanied by a 95% exact binomial confidence interval. Possible baseline demographic and clinical predictors of such toxicity may be evaluated by means of logistic regression, but, due to the low expected number of such toxicities, any such modeling will be strictly exploratory.

21.3.4 **Secondary Objective 1** *Conduct normal mucosa EGFR assessment for comparison with tumor sample.* The change in tumor EGFR level across treatment, relative to EGFR in normal mucosa, will be evaluated by means of repeated measures ANOVA.

21.3.5 **Secondary Objective 2** *Correlate HPV presence and titer with p53 status and clinical outcome.* HPV status ( $\pm$ ) will be added to the models of Primary Objective 2 to determine if +HPV patients respond to therapy differently than -HPV patients, but, due to the limited expected number of +HPV patients, such analyses will be considered exploratory.

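### Section 21.3.1 makes an open-ended search for baseline factors related to marker change a primary question, with no alpha, factor list, error control or exploratory label

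*Combined protocol and SAP*

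**What the plan says.** Section 21.3.1 of the combined protocol and SAP sets two primary questions for Primary Objective 1. The first is whether the loading dose modulates each marker. The second is "are there baseline clinical or demographic variables that are related to significant variation in biomarker response to the loading dose of cetuximab".

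For continuous markers the method is stated in one sentence: "The second question will be answered by means of analysis of variance on baseline clinical and demographic variables". For dichotomous markers, Wald tests are used to see whether "any subset of patients defined by clinical or demographic factors have proportions significantly different from 0.5", and ordinal markers are treated similarly. The factors are not named, and the text does not say whether each factor is tested separately or one overall test is made per marker.

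The marker list is open. Section 13.5 names "p-EGFR and total EGFR, p-ERK1/2, p-AKT, p27, Ki-67, and p-STAT3, and other markers that we may discover in our preclinical studies". Appendix B, under high-throughput immunoblotting, adds further named proteins and leaves room for novel ones.

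Two other analyses in section 21.3 are labelled. Baseline predictors of toxicity (21.3.3) carry the words "any such modeling will be strictly exploratory", and the HPV models (21.3.5) carry "such analyses will be considered exploratory". Section 21.3.1 has no such label. The only significance level in section 21 is the 0.05 in 21.4, which belongs to the single-marker power simulation for Objective 2.

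**The concern.** The second question is a search over markers times factors, and its answer is whichever pairs reach significance. With the factors unlisted and the markers open-ended, the size of the search is unknown in advance and nothing limits false findings. If the plan is followed as written, a statement that age or performance status, for example, is related to marker response could be reported as a primary result on one unadjusted test in 50 patients.

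This is a different family from the marker-outcome tests of 21.3.2. Here marker change is the outcome and patient characteristics are the predictors, so error control written for 21.3.2 would not reach it. The conclusion matters because section 21.4 describes a screen for patients likely to benefit as desirable, and a chance finding about which patients show a marker response could feed that aim.

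**Working it through.** **The plan's own figure.** The documents give no error rate, power or test count for Objective 1. The only design figure is in 21.4 and concerns Objective 2: at least 80% power for one marker at an effect of 1.1 standard units. It reproduces: simulated Cox tests with 50 patients, median 22 months, 36 months' accrual and 6 months' follow-up (about 25 events) give 85% at 1.1 with the SD taken within groups, and 94% with the overall SD. It has no bearing on this point.

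**Inputs from the documents**
- Patients: "Fifty evaluable patients will be accrued to the trial" (21.2).
- Markers in section 13.5: 7 named.
- Markers in Appendix B: phospho and total forms of four proteins (8), plus p27, PARP and Bcl-XL, so 11. Section 13.5 adds p-ERK1/2 and Ki-67, so the union is 11 + 2 = 13. Novel markers are not counted.

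**Assumptions, because the plan is silent**
- 0.05 per test, two-sided, and no true relation anywhere (a global null).
- Four factors, taking as examples the four eligibility routes in section 3.2: age, co-morbidity, KPS and creatinine clearance. The plan does not say that these are the factors. One and two factors are also shown.
- Factors split 50:50; continuous, normally distributed marker changes.

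**Step 1: tests and expected false findings, factor by factor**
- 7 × 4 = 28 tests; 28 × 0.05 = 1.4 expected.
- 13 × 4 = 52 tests; 52 × 0.05 = 2.6 expected.

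The expected counts do not depend on correlation.

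**Step 2: chance of at least one false finding, independent tests**

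P = 1 − 0.95^k
- k = 28: 1 − 0.238 = 76.2%
- k = 52: 1 − 0.069 = 93.1%
- P passes 50% at k = 14 (13 tests 48.7%, 14 tests 51.2%).

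**Step 3: correlated markers**, by simulation with n = 50. The table comes from 20,000 trials per cell with independent factors.

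| Markers × factors | Correlation 0 | 0.5 | 0.8 |
|---|---|---|---|
| 7 × 4, one by one | 76% | 65% | 48% |
| 13 × 4, one by one | 93% | 80% | 58% |
| 7 × 2, one by one | 52% | 42% | 28% |
| 13 × 2, one by one | 74% | 56% | 36% |
| 7 × 1 | 30% | 23% | 15% |
| 13 × 1 | 49% | 34% | 20% |

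If the factors are themselves modestly correlated (0.3 on the underlying scale), the four-factor values at 0.8 become 46% and 56.5%. I therefore quote about 48% for 7 markers and 56% for 13 as the lower ends; each is good to about two percentage points.

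**Step 4: one overall F test per marker**
- Independent markers: 1 − 0.95^7 = 30.2%; 1 − 0.95^13 = 48.7%.
- Correlation 0.8, four factors, simulated: about 16% and 21%.

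Simulating the uncorrelated cases can land a point or two off the closed form (one run gave 78%, 94%, 31% and 51%), so I quote the closed-form values for the upper ends.

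**Not covered.** For dichotomous markers the plan tests subset proportions against 0.5. That is not a test of no relation between factor and response, so none of these percentages describes those tests or the ordinal ones.

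**The case against.** The strongest reply is that the size of the problem depends on choices the plan does not make. The text refers to general linear models and analysis of variance, and one multi-factor model per marker with a single overall test is a natural reading. The chance of a false finding then stays below one half. With one or two factors and correlated markers it is often below one half too. No alpha is stated for Objective 1, so 0.05 is borrowed. All of this stands, and it rules out a flat claim that a false finding is more likely than not. It does not supply error control: the lowest case examined is about 15%, three times 5%.

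A second reply is that the exploratory labels in 21.3.3 and 21.3.5 rest on sparse data (few toxicities, few HPV-positive patients) and not on multiplicity. That is right. The absence of a label in 21.3.1 therefore does not contradict a principle stated by the plan. It shows only that nothing in section 21 downgrades this question.

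A third reply is that no decision depends on the answer. Sample size rests on Objective 2, all patients receive the same treatment, and the particular interest in 21.3.2 is in markers picked out by the first question. That also stands and limits the consequence to what is reported. The question is still designated primary, and its result would be read as such.

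**Conclusion.** The concern holds in a conditional form. Section 21.3.1 gives primary status to a significance search whose factors are unnamed and whose markers are open-ended, with no alpha, error control or exploratory label.

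Under the stated assumptions, four factors tested singly give about 48% to 76% (7 markers) or 56% to 93% (13 markers), and one overall F test per marker gives about 16% to 30% or 21% to 49%. Every case is well above 5%, and the spread is itself a result of the plan leaving the family undefined.

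A reader might infer three stronger things that the documents do not support. One is that a false finding is more likely than not in general; that needs roughly three or four factors tested one by one, and it can fail with strongly correlated markers. Another is that every factor will be tested against every marker; the text names no factors and does not fix the testing scheme. The third is that the trial will declare a patient subset responsive or act on it; no such rule is written.

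**What to change.** In section 21.3.1, keep modulation by the loading dose as the primary question and move the baseline-factor question out of the primary set. State that:

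- analyses relating marker change to baseline clinical and demographic factors, including the subset tests for dichotomous and ordinal markers, are exploratory;
- the markers and factors are listed and fixed before analysis;
- results are given as estimates with 95% confidence intervals, with p-values adjusted by the Benjamini-Hochberg method across that marker-by-factor grid at a false discovery rate of 10%;
- no subset is declared more or less responsive on an unadjusted p-value.

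The list has to come with the adjustment, because a grid that is not fixed cannot be adjusted for in advance. The label alone would correct the status of the question; the adjustment keeps the reported p-values interpretable.

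The cost is wording, one list and one extra analysis step, with no added patients, visits or assays. The downside is that a factor with only an unadjusted p below 0.05 can no longer be reported as a primary finding. A single isolated signal would need p at or below 0.10/28 = 0.0036 with 28 tests, or 0.10/52 = 0.0019 with 52. This change does not address multiplicity across markers in the modulation test itself.

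### Section 21.3.1 allows, with no rule for choosing, a percent-of-baseline test of marker modulation that is biased towards increases when the baseline biopsy is measured with error

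*Combined protocol and SAP*

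**What the plan says.** Primary Objective 1 (section 21.3.1) asks of each marker: "is the marker modulated by the loading dose of cetuximab". For continuous markers, "the null hypothesis that the mean value of the change (absolute or percent of baseline) equals zero will be tested", by a one-sample t-test. Both scales are offered in one parenthesis, and nothing says which applies to which marker.

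Transformation is mentioned earlier in the same section: "The initial analysis will use descriptive and graphical statistics to determine if any of the markers require transformation prior to analysis". It is then permitted but not required, and no log scale is named.

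On sample size, section 21.2 says: "Fifty evaluable patients will be accrued to the trial, which is expected to take 36 months".

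Two kinds of continuous measure are described in Appendix B. For immunoblots, "The films then will be scanned, and the bands analyzed using NIH ImageJ software", with each antibody probed in duplicate. For the TMA, each core is scored from 1 to 4 and the cores from one subject are averaged into a continuous score. No section gives a biopsy-to-biopsy standard deviation or CV for any marker.

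Under section 21.3.2 every marker goes into the outcome models, and those found to be modulated receive extra attention.

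**The concern.** A percent change has a measured quantity in its denominator. When the baseline reads low by chance, the ratio is inflated by more than it is deflated when the baseline reads high by the same factor. The average ratio is therefore above 1 with no drug effect. A t-test centred on zero percent change treats that excess as evidence of an increase.

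Error of this kind is plausible here. The specimens are punch biopsies of about 3 mm, the second-visit cores come from different areas of the tumour (section 13.5), and the immunoblot readout is film densitometry.

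Two things are at stake. A marker that did not move could be reported as raised. A modest true fall, which is the direction the study hypothesises for EGFR and its downstream signals, could be missed because the upward bias offsets it.

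**Working it through.** **The plan's own figure.** There is no power or error calculation for this test. The only power figure, in section 21.4, concerns Primary Objective 2: at least 80% at an effect of 1.1 SD. It reproduces at 83-84% with about 25 events (effect scaled by the within-group SD), and it does not bear on this point.

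**Inputs.** From the documents: n = 50 (section 21.2) and a one-sample t-test, so 49 degrees of freedom (section 21.3.1). Assumed: two-sided 0.05, because section 21.3.1 states neither level nor sidedness; independent lognormal error with the same CV at both biopsies, over the range 0.1 to 0.5; between-patient log-SD 0.6, which affects only the absolute-change results.

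**Step 1, the bias.** Write pre = T·exp(e1) and post = k·T·exp(e2), where T is the patient's true level, k the true post/pre ratio, and e1, e2 are independent N(0, s²) with s² = ln(1 + CV²). Then post/pre = k·exp(e2 - e1), and T cancels. Since e2 - e1 has variance 2s², the mean ratio is k·exp(s²) = k(1 + CV²). Hence

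mean percent change = 100 × [k(1 + CV²) - 1].

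With no effect (k = 1) this equals 100 × CV².

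**Step 2, bias against standard error.** For k = 1 the SD of the ratio is (1 + CV²)·√[(1 + CV²)² - 1]. At CV 0.4 this is 1.16 × √(1.3456 - 1) = 0.682, so the standard error is 0.682/√50 = 0.096. The bias of 0.16 is about 1.66 standard errors. A normal approximation gives P(Z > 1.96 - 1.66) = P(Z > 0.30), about 38%. Simulation gives a little less because the ratio is skewed.

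**Step 3, rejection with no true change** (simulated; repeat runs agree to about a point):

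| CV | Mean percent change | Percent-change test rejects | Log ratio rejects |
|---|---|---|---|
| 0.1 | +1% | 7% | 5% |
| 0.2 | +4% | 13% | 5% |
| 0.3 | +9% | 22% | 5% |
| 0.4 | +16% | 34% | 5% |
| 0.5 | +25% | 44% | 5% |

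From CV 0.2 up, nearly all of the percent-change rejections are increases. Absolute change rejects in 4-5% throughout.

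**Step 4, power for a true 20% decrease** (k = 0.8):

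| CV | Mean percent change | Power, percent change | Power, log ratio |
|---|---|---|---|
| 0.2 | 0.8 × 1.04 - 1 = -16.8% | 99% | 100% |
| 0.3 | 0.8 × 1.09 - 1 = -12.8% | 65% | 96% |
| 0.4 | 0.8 × 1.16 - 1 = -7.2% | 22% | 81% |

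At CV 0.5 the mean is 0.8 × 1.25 - 1 = 0, so the bias exactly cancels the fall. Absolute change at CV 0.4 has about 65% power with the assumed between-patient log-SD of 0.6, and 79% down to 47% as that spread goes from 0 to 1.0.

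For a true 50% decrease at CV 0.5, the mean percent change is 0.5 × 1.25 - 1 = -37.5%, and the percent-change test keeps about 99% power.

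**Step 5, TMA scores.** The lognormal model does not suit a score bounded at 1 and 4. With additive error of SD 0.2, 0.4, 0.6 and 0.8 and no true change, the percent-change test rejects in about 6%, 10%, 17% and 25% of trials. Absolute change stays at 4.8-5.1%.

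**The case against.** The strongest reply is that the plan already contains a sound route. It offers absolute change, which holds its level, and it allows transformation. Absolute change of a log-transformed marker is the log ratio. This stands, and a reader who inferred that the plan commits to percent change would be wrong. But permission to transform neither names a scale nor withdraws the percent option, so one stated route still gives a misleading answer.

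Second, the t-test is roughly valid for its literal null, a mean percent change of zero. That is also true. The fault is that this null is not the question section 21.3.1 asks.

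Third, the size depends on a variability the documents do not supply, and duplicate probing and core averaging reduce measurement noise. Both hold: at CV 0.1 the inflation is only about two points. Replication does not remove sampling differences between two biopsies a week or more apart.

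Three stronger readings are tempting and unsupported:

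- That true EGFR decreases are hidden in general. Only falls that are small relative to the noise are lost; large ones are found.
- That this test decides which markers reach Primary Objective 2. Section 21.3.2 analyses all of them, so the effect is on emphasis only, and a false increase would not be read as the hypothesised inhibition.
- That the scale will be picked after the data are seen. The text does not say when absolute or percent is chosen.

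**Conclusion.** The point holds as a defect in one of two permitted analyses, together with the absence of a rule for choosing. The direction of the bias is certain whenever the baseline carries error independent of the second reading. Its size is not known: false declarations of modulation run from about 7% to 44% over CV 0.1 to 0.5 under the lognormal assumption, and from about 6% to 25% on the TMA score. All of these figures assume 50 patients, a two-sided 0.05 test and equal error at both biopsies.

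The consequence is limited to the continuous-marker answer under Primary Objective 1 and the priority given to markers afterwards. The sample-size justification in section 21.4 is unaffected. It should be corrected before the marker data are analysed, because the correction is right at any CV.

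**What to change.** In section 21.3.1, remove percent of baseline as a test scale and name the scale for each type of measure:

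- For continuous intensity measures such as immunoblot densitometry, test ln(post) - ln(pre) against zero with the one-sample t-test. Report the back-transformed geometric mean ratio with its 95% confidence interval.
- For averaged 1-4 TMA scores, test absolute change.
- State the level and sidedness of the test. Percent change may still be shown descriptively.

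This costs a sentence or two and needs no new data, visits or patients. The real cost lies with undetectable readings. The log ratio is undefined if either reading is zero, and a strongly suppressed phosphoprotein band may be just such a case. A floor value therefore has to be fixed in advance for each assay, with a sensitivity analysis that varies it.
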